- Valve-related dysfunction requiring repeat procedure (BAV, TAVI, or SAVR)
- All-cause death

Early safety composite endpoint-incidence estimates will be provided for the two treatment groups at 30 days. The statistical method will be the Bayesian version of a comparison of proportions.

5. Incidence of Clinical Efficacy (after 30 days) at 6 months, 12 months, 18 months, 24 months and annually thereafter up to 5 years. Clinical efficacy defined as a composite of:
- All-cause mortality
  - All stroke (disabling and non-disabling)
  - Requiring hospitalizations for valve-related symptoms or worsening congestive heart failure
  - NYHA class III or IV
  - Valve-related dysfunction (mean aortic valve gradient  $\geq 20$  mmHg, EOA  $\leq 0.9$ - $1.1$   $\text{cm}^2$  and/or DVI  $< 0.35$  m/s, AND/OR moderate or severe prosthetic valve regurgitation\*)

Clinical efficacy estimates will be provided for the two treatment groups at 6 months, 12 months, 18 months, 24 months and annually thereafter up to 5 years. The statistical method will be the Bayesian version of a comparison of proportions (with predictions).

\*Refers to VARC-2 definitions

6. Incidence of Time-Related Safety at 30 days, 6 months, 12 months, 18 months, 24 months and annually thereafter up to 5 years. Time-Related Safety defined as a composite of:
- Structural valve deterioration:
    - Valve-related dysfunction (mean aortic valve gradient  $\geq 20$  mmHg, EOA  $\leq 0.9$ - $1.1$   $\text{cm}^2$  and/or DVI  $< 0.35$  m/s, AND/OR moderate or severe prosthetic valve regurgitation\*)
    - Requiring repeat procedure (TAVI or SAVR)
  - Prosthetic valve endocarditis
  - Prosthetic valve thrombosis
  - Thromboembolic events (eg. stroke)
  - VARC bleeding, unless clearly unrelated to valve therapy (eg. trauma)

Time related safety composite endpoint-incidence estimates will be provided for the two treatment groups at 30 days, 6 months, 12 months, 18 months, 24 months and annually thereafter up to 5 years. The statistical method will be the Bayesian version of a comparison of proportions (with predictions).

\*Refers to VARC-2 definitions

7. Conduction disturbance requiring permanent pacemaker implantation at 30 days, 6 months, 12 months, 18 months, 24 months, and annually thereafter up to 5 years.

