12. Echocardiographic assessment of prosthetic valve performance at discharge, 6 months, 12 months, 24 months, and annually thereafter up to 5 years using the following measures:

- transvalvular mean gradient
- effective orifice area
- degree of prosthetic aortic valve regurgitation (including transvalvular and paravalvular)

The four echocardiographic measurements will be evaluated at discharge, 6 months, 12 months, 24 months, and annually thereafter up to 5 years. All implanted subjects undergoing echocardiography procedures will be evaluated.

Continuous measures will be evaluated using a Bayesian version of a two-sample t-test. Categorical variables will be evaluated using Bayesian version of a comparison of polytomous outcomes.

Additionally, incidence of moderate/severe aortic insufficiency at discharge will be compared between groups using the Bayesian version of a comparison of proportions.

13. Aortic valve disease related hospitalizations

The number of subjects re-hospitalized after the initial index procedure will be compared at 30 days, 6 months, 12 months, 18 months, 24 months, and annually thereafter up to 5 years.

Incidence of recurrent hospitalization will be provided at 30 days, 6 months, 12 months, 18 months, 24 months, and annually thereafter up to 5 years. The statistical method will be the Bayesian version of a comparison of proportions (with predictions).

14. Cardiovascular deaths and valve-related deaths

The number of subjects experiencing cardiovascular deaths and valve-related deaths at 30 days, 6 months, 12 months, 18 months, 24 months, and annually thereafter up to 5 years. Incidences will be compared between groups. The statistical method will be the Bayesian version of a comparison of proportions (with predictions).

15. Strokes and TIAs

The number of subjects with strokes (of any severity) and TIAs at 30 days, 6 months, 12 months, 18 months, 24 months, and annually thereafter up to 5 years. A separate analysis will be performed for each of the following:

- a composite of all strokes and TIAs
- disabling strokes only
- non-disabling strokes only
- TIAs only

The statistical method will be the Bayesian version of a comparison of proportions (with predictions).

Additionally, incidence of all strokes at 30 days or hospital discharge, whichever is longer, will be compared between groups using the Bayesian version of a comparison of proportions.

16. Peri-procedural Neurological Injury (Stroke, TIA, Encephalopathy)

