## RECURRENT HOSPITALIZATION

Recurrent hospitalization is defined as a non-elective hospital admission for signs and symptoms related to aortic valve disease (as described below), as well as complications related to aortic valve procedures including neurological events, infection, additional procedures (eg. implant of permanent pacemaker), and renal failure. For the purposes of the protocol a hospitalization is an admission that results in at least a one night stay (i.e., one midnight/change in calendar day).

Overnight stays at nursing home facilities, extended care facilities, or emergency room visits that do not result in an in-patient admission do not meet the protocol definition of recurrent hospitalization. Patients with signs and symptoms related to aortic valve disease (as described below) who are hospitalized for less than one night or who are treated and released from the emergency department or an outpatient clinic [including treatment for intravenous heart failure therapy (eg., inotropes, diuretics, and/or vasodilators)], does not meet the protocol definition of as recurrent hospitalizations.

Aortic valve disease will be evaluated using documented evidence of the following signs and symptoms. An independent Clinical Events Committee (CEC) will review all available source documentation for all hospitalizations to determine if they are aortic valve disease hospitalizations. The CEC adjudication will be used for final analysis.

Signs and Symptoms of Aortic Valve Disease	
Sign/Symptom	Definition
Aortic Valve Dysfunction	
Shortness of breath/dyspnea	A feeling of difficult or labored breathing that is out of proportion to the patient's level of physical activity
Exercise intolerance	A condition where the patient is unable to do physical exercise at the level or for the duration that would be expected of someone in his/her general physical condition, or experiences unusually severe post-exercise pain, fatigue, or other negative effects
Dizziness/syncope	Lightheadness or unsteadiness of gait or a partial or complete loss of consciousness with interruption of awareness of oneself and ones surroundings
Chest pain	Discomfort and soreness in and around the chest
Worsening Heart Failure	
Volume Overload	
Orthopnea	Dyspnea in which the person can breathe comfortably only when standing or sitting erect

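### Secondary endpoint 13 has two incompatible event sets: the O.2 definition counts readmissions for procedure complications, but the CEC question that fixes the final analysis does not

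*Combined protocol and SAP*

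**What the plan says.** **Endpoint 13, C.6.8.1.** The heading is "Aortic valve disease related hospitalizations", and the list of inferential endpoints in C.6.7.2 repeats that label. The comparison sentence reads "The number of subjects re-hospitalized after the initial index procedure will be compared at 30 days" and goes on to later time points. The next sentence changes the term: "Incidence of recurrent hospitalization will be provided at 30 days", again continuing to 5 years.

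**Recurrent Hospitalization, O.2.** This is the only formal definition of the reported term, and it has two limbs.

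- Limb 1: "Recurrent hospitalization is defined as a non-elective hospital admission for signs and symptoms related to aortic valve disease".
- Limb 2: "as well as complications related to aortic valve procedures including neurological events, infection, additional procedures (eg. implant of permanent pacemaker), and renal failure".

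A length-of-stay rule also applies: "a hospitalization is an admission that results in at least a one night stay". Emergency-room, outpatient and nursing-facility care without an inpatient admission is excluded.

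**Adjudication, same O.2 entry.** Valve disease is to be judged from a table of signs and symptoms. The CEC then reviews source documents "for all hospitalizations to determine if they are aortic valve disease hospitalizations. The CEC adjudication will be used for final analysis". Limb 2 is not mentioned in that instruction.

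**The concern.** The definition and the adjudication rule should select the same admissions, and here they do not. The definition admits procedure complications. The question put to the CEC asks about valve disease only, and its answer is what enters the analysis. A statistician following the definition and one following the adjudicated dataset would count different subjects.

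The admissions in dispute are consequences of the procedures being compared, so their frequency may differ between the arms. Endpoint 13 is compared at 30 days, at 6, 12, 18 and 24 months, and at years 3, 4 and 5. That is 5 + 3 = 8 time points, and the mismatch carries into each of them.

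**Working it through.** The plan states no rate, power or margin for endpoint 13, so there is no figure to reproduce. The check is to classify test admissions under each wording. All are assumed to occur after the index procedure and to last at least one night.

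| Admission | Heading and CEC question | O.2 definition |
|---|---|---|
| Non-elective, for dyspnea or worsening heart failure | Event | Event |
| Non-elective, for a procedure complication, with no listed valve-disease sign (e.g. wound infection) | Not an event | Event |
| Elective, or unrelated to valve or procedure | Not an event | Not an event |

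The second row is the contradiction. It arises inside the single O.2 entry, so naming O.2 as the governing text does not resolve it.

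**Which admissions fall in the second row.** The table of signs in O.2 is broad. It includes dizziness or syncope, dyspnea, chest pain, hypotension, and renal dysfunction shown by a 25% rise in creatinine. A pacemaker readmission presenting with syncope, or a renal readmission with raised creatinine, could therefore qualify as valve disease too. The clear cases are complications with none of the listed signs: an infection without them, or a pacemaker readmission without them.

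**What moves the comparison.** Endpoint 13 counts subjects, not admissions. For each arm:

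- let v be the proportion with at least one valve-disease readmission;
- let c be the proportion whose only qualifying readmissions are procedure complications without listed signs.

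Using subscripts T for TAVI and S for SAVR:

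- CEC rule: difference = v_T − v_S
- O.2 definition: difference = (v_T + c_T) − (v_S + c_S)
- Change from one to the other: c_T − c_S

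Subjects with both kinds of readmission count either way and do not contribute to the change. Different complications may predominate in the two arms and partly offset each other. The documents give neither c_T nor c_S. The 30% bound in labeling objective 18 (C.6.10.1) concerns new pacemaker implants in the TAVI arm, not readmissions, and cannot stand in for either.

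**The case against.** The strongest defence is that there is one formal definition, endpoint 13 uses its term, and the CEC sentence within it is shorthand for adjudicating that defined event. This is a possible reading, but the text does not favour it. Just before the CEC instruction, O.2 ties valve disease to the table of signs and symptoms. The CEC's question therefore points to limb 1, and nothing asks it to record limb 2.

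A second defence is that the CEC charter (C.5.3) must set explicit classification rules before adjudication, and C.6.5.2 leaves further analysis detail to the SAP. Either may settle the scope. The text reviewed is one part of four and contains neither the charter nor any SAP text on endpoint 13. That limits the certainty of the point, but the protocol's own sentences would still need to agree.

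A third is that little depends on it, because several of the disputed complications are reported elsewhere: pacemaker (endpoint 7), acute kidney injury within MAE (endpoint 3), stroke and TIA (endpoint 15). This stands and keeps the point modest.

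Two wider readings do not hold.

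- A reader might infer a third, any-cause definition from the comparison sentence. The heading and the C.6.7.2 label limit that sentence, and endpoint 10 says explicitly that all hospitalizations count when that is meant. The sentence is loose, but it is not a rival definition.
- A reader might add the hospitalization component of endpoint 5, "Requiring hospitalizations for valve-related symptoms or worsening congestive heart failure". That belongs to a separate composite with its own wording and does not contradict endpoint 13.

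**Conclusion.** The point holds as a conflict between two event sets. Followed as written, the adjudication rule drops readmissions that the plan's own definition of the reported term includes. The number affected is unknown. It is restricted to subjects whose only qualifying readmissions are procedure complications without a listed valve-disease sign.

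The consequence is limited. Endpoint 13 is secondary and is not in the testing sequence of C.6.10 and C.6.10.1, so no labeling claim rests on it. The primary endpoint is untouched.

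Two stronger conclusions might be drawn, and the documents support neither. One is that the choice of event set could reverse the direction of the difference; without rates for either arm this cannot be shown. The other is that, because treatment is open-label and the sponsor's statistics department runs the analysis, the event set would be picked once results were known. The CEC is independent and must write its rules before it adjudicates, and nothing shows a later choice.

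The conclusion assumes that neither the CEC charter nor the SAP already directs the CEC to code both limbs.

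**What to change.** 1. In endpoint 13, replace the re-hospitalized wording with: subjects with at least one CEC-adjudicated recurrent hospitalization per O.2. The heading then serves as a short title and no longer sets the scope.
2. In O.2, change the CEC sentence so that the committee classifies each admission on both limbs: valve-disease signs and symptoms, and complication of the valve procedure.
3. Report the two limbs separately beside the combined endpoint, so that a reader can see which one drives any difference.

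The cost is two wording changes in the protocol, with matching text in the SAP and charter, plus one additional code. O.2 already has the CEC reviewing source documents for every hospitalization, so no new data collection is needed. Any admission already adjudicated on the narrower question would need the second code added.

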For each treatment group, the proportion of subjects with a neurologic injury (stroke, TIA, or encephalopathy) at discharge or at 7 days post-index procedure (whichever occurs first) will be calculated. The numerator will be the number of subjects with a neurologic injury (stroke, TIA, or encephalopathy) at discharge or at 7 days post-index procedure (whichever occurs first), and the denominator will be the number of subjects in that treatment group. Results will also be presented separately for disabling stroke, non-disabling stroke, TIA, and encephalopathy. Proportions will be compared between groups using Bayesian version of a comparison of proportions.

17. Index procedure related MAEs

Index procedure-related MAE events will be summarized and event rates will be provided at 30 days. The numerator will be the number of procedure-related MAE events experienced by the end of the 30-day follow-up visit, and the denominator will be the number of subjects evaluated at the 30-day follow-up visit (or a later follow-up) plus the number of subjects not evaluated but who experienced a procedure-related MAE event prior to the end of the follow-up visit window.

The endpoint is descriptive and no statistical hypothesis test will be performed.

18. Length of index procedure hospital stay

The length of TAVI or SAVR hospital stay will be summarized for all subjects undergoing a trial procedure.

The endpoint will be evaluated between groups using a Bayesian version of a t-test.

19. Presence of atrial fibrillation at post-procedure, discharge, 30 days, 6 months, 12 months, 18 months, 24 months, and annually thereafter up to 5 years.

The statistical method will be the Bayesian version of a comparison of proportions (with predictions).

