where  $\mu_{TAVI}$  and  $\mu_{SAVR}$  denote the mean improvements in the KCCQ score from baseline to 30 days. For subjects with KCCQ score at both baseline and 30 days, the improvement in KCCQ will be calculated as  $KCCQ_{30day} - KCCQ_{baseline}$ . This objective will be evaluated using a Bayesian version of a two-sample t-test (see Section C.11). The posterior probability  $P(H | data)$  will be calculated and compared to a threshold of 0.95.

5. Length of index procedure hospital stay after TAVI vs. SAVR (secondary objective #18). The hypothesis of interest is

$$H: \mu_{TAVI} < \mu_{SAVR}$$

where  $\mu_{TAVI}$  and  $\mu_{SAVR}$  denote the mean length of index hospital stay. This objective will be evaluated using a Bayesian version of a two-sample t-test (see Section C.11). The posterior probability  $P(H | data)$  will be calculated and compared to a threshold of 0.975.

6. Transvalvular mean gradient at 12 months (superiority): TAVI vs. SAVR (secondary objective #12). The hypothesis of interest is

$$H: \mu_{TAVI} < \mu_{SAVR}$$

where  $\mu_{TAVI}$  and  $\mu_{SAVR}$  denote the average mean gradient from at 12 months, measured in mmHg. This objective will be evaluated using a Bayesian version of a two-sample t-test (see Section C.11). The posterior probability  $P(H | data)$  will be calculated and compared to a threshold of 0.975.

7. Effective orifice area at 12 months (superiority): TAVI vs. SAVR (secondary objective #12). The hypothesis of interest is

$$H: \mu_{TAVI} > \mu_{SAVR}$$

where  $\mu_{TAVI}$  and  $\mu_{SAVR}$  denote the mean effective orifice area at 12 months, measured in  $cm^2$ . This objective will be evaluated using a Bayesian version of a two-sample t-test (see Section C.11). The posterior probability  $P(H | data)$  will be calculated and compared to a threshold of 0.975.

8. Change in Kansas City Cardiomyopathy Questionnaire (KCCQ) score from baseline to 30 days (superiority): TAVI vs. SAVR (secondary objective #11). The hypothesis of interest is

$$H: \mu_{TAVI} > \mu_{SAVR}$$

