13. Incidence of MACCE at 30 days or hospital discharge, whichever is longer: TAVI vs. SAVR (secondary objective #1). The hypothesis of interest is

$$H: \pi_{TAVI} < \pi_{SAVR}$$

where  $\pi_{TAVI}$  and  $\pi_{SAVR}$  denote the binary rate of MACCE at 30 days or hospital discharge (if longer). The posterior probability  $P(H | \text{data})$  will be calculated and compared to a threshold of 0.975. The statistical method will be the Bayesian version of a comparison of proportions (see Section C.11).

14. Incidence of major vascular complications at 30 days or hospital discharge, whichever is longer: TAVI vs. SAVR (secondary objective #3). The hypothesis of interest is

$$H: \pi_{TAVI} < \pi_{SAVR}$$

where  $\pi_{TAVI}$  and  $\pi_{SAVR}$  denote the binary rate of major vascular complications at 30 days or hospital discharge (if longer). The posterior probability  $P(H | \text{data})$  will be calculated and compared to a threshold of 0.975. The statistical method will be the Bayesian version of a comparison of proportions (see Section C.11).

15. Incidence of major or life-threatening bleeding event at 30 days or hospital discharge, whichever is longer: TAVI vs. SAVR (secondary objective #3). The hypothesis of interest is

$$H: \pi_{TAVI} < \pi_{SAVR}$$

where  $\pi_{TAVI}$  and  $\pi_{SAVR}$  denote the binary rate of major or life-threatening bleeding events at 30 days or hospital discharge (if longer). The posterior probability  $P(H | \text{data})$  will be calculated and compared to a threshold of 0.975. The statistical method will be the Bayesian version of a comparison of proportions (see Section C.11).

16. Incidence of all strokes at 30 days or hospital discharge, whichever is longer: TAVI vs. SAVR (secondary objective #15). The hypothesis of interest is

$$H: \pi_{TAVI} < \pi_{SAVR}$$

where  $\pi_{TAVI}$  and  $\pi_{SAVR}$  denote the binary rate of strokes at 30 days or hospital discharge (if longer). The posterior probability  $P(H | \text{data})$  will be calculated and compared to a threshold of 0.975. The statistical method will be the Bayesian version of a comparison of proportions (see Section C.11).

17. Incidence of moderate/severe aortic insufficiency after TAVI vs. SAVR (secondary objective #12). The hypothesis of interest is

$$H: \pi_{TAVI} < \pi_{SAVR}$$

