### **D.2 Potential Benefits**

Patients treated with TAVI may experience improvement in quality of life, morbidity and mortality compared to traditional open-heart aortic valve replacement. Potential benefits include, but are not limited to, absence of open-heart surgery-related risks, reduced procedure time, reduced anesthesia procedure time, shorter hospital stay and earlier return to normal activities than after open-heart aortic valve replacement.

There is no direct benefit associated to participation in this trial, but the information obtained during this trial will be used scientifically. The results of this trial can help physicians understand the implications of transcatheter treatment of patients with intermediate risk for surgery.

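### Endpoint 16 stops counting neurological injury at the earlier of discharge and day 7, so the arm expected to leave hospital sooner is counted over fewer days

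*Combined protocol and SAP*

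**What the plan says.** Endpoint 16 in C.6.8.1 covers peri-procedural neurological injury: stroke, TIA or encephalopathy. The proportion "at discharge or at 7 days post-index procedure (whichever occurs first) will be calculated", and "the denominator will be the number of subjects in that treatment group". The comparison is inferential: "Proportions will be compared between groups using Bayesian version of a comparison of proportions". C.6.7.2 also lists this endpoint among those that receive inferential statistics. By contrast, endpoint 17, the next in the list, is declared descriptive. Results for endpoint 16 are also shown separately for disabling stroke, non-disabling stroke, TIA and encephalopathy.

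On length of stay, D.2 lists among the potential benefits of TAVI "shorter hospital stay and earlier return to normal activities than after open-heart aortic valve replacement". C.6.10.1 item 5, "Length of index procedure hospital stay after TAVI vs. SAVR", tests a shorter mean stay against a posterior threshold of 0.975.

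Other early comparisons use a longer window. An example is the "incidence of all strokes at 30 days or hospital discharge, whichever is longer" under endpoint 15. C.5.2 has all new or worsening adverse events recorded through the 24-month visit.

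**The concern.** The counting window closes at an event that treatment influences. Take an encephalopathy on day 6. It counts for a SAVR subject still in hospital, but not for a TAVI subject discharged on day 4. The denominator includes both subjects in full, and nothing in the protocol text reviewed adjusts for days observed. If the trial's own length-of-stay hypothesis is true, the arms are compared over unequal time at risk, and on a cumulative count the shortfall falls on the TAVI side.

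At stake is the credibility of a neurological safety comparison. A lower TAVI proportion could reflect less injury, earlier discharge or both, and the planned analysis could not separate them.

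**Working it through.** The plan gives no rate, stay or power for endpoint 16, so there is no stated figure to reproduce. The check gives both arms the same true risk and asks what the endpoint would show.

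**From the documents**
- 1600 mITT subjects randomised 1:1 (C.6.5.2), taken as 800 per arm.
- Beta(1,1) priors, borrowed from the primary analysis.
- A threshold of 0.975, borrowed from the proportion endpoints in C.6.10.1. Endpoint 16 states no threshold.

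**Assumed, not in the documents**
- R: true 7-day risk, equal in both arms.
- e: share of events on days 0–1, with the rest uniform to day 7.
- L: length of stay, lognormal with log-scale SD 0.40–0.45.

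**Formula.** For a stay of L days (L at least 1), the captured share is e + (1 − e) × (min(L, 7) − 1)/6. The observed proportion is R times this share, averaged over stays.

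**Simple case, fixed stays.** R = 5%, TAVI discharged on day 3, SAVR observed for all 7 days.
- Uniform timing: 5% × 3/7 = 2.1% v 5.0%. The posterior passes 0.975 in about 88% of trials.
- e = 0.5: 5% × (0.5 + 0.5 × 2/6) = 3.3% v 5.0%; about 38%.
- e = 0.8: 5% × (0.8 + 0.2 × 2/6) = 4.3% v 5.0%; about 9%.
- e = 0.95: 5% × (0.95 + 0.05 × 2/6) = 4.8% v 5.0%; about 3%.
- Both arms observed for 7 days: 5.0% v 5.0%; about 2.4%.

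**Varying stays, worked example.** R = 12%, e = 0.5, median stays 4 v 8 days. The average captured share is 77% v 95%. Observed proportions are 12% × 0.768 = 9.2% and 12% × 0.952 = 11.4%, a spurious 2.2 points. The chance of passing 0.975 is about 30%.

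**Ranges**

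| Risk | Share on days 0–1 | Median stay, TAVI v SAVR | Spurious difference | Chance of passing 0.975 |
|---|---|---|---|---|
| 8–12% | 50–70% | 4–6 v 8–9 days | 0.3–2.4 points | 4–35% |
| 3–5% | 90% | 4–6 v 8–9 days | 0.04–0.2 points | 3–4% |

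The smallest value in the first row comes from R = 8%, e = 0.7 and medians 6 v 8: 8 × (0.967 − 0.930) = 0.3 points. The largest comes from R = 12%, e = 0.5 and medians 4 v 9: 12 × (0.969 − 0.768) = 2.4 points.

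**Check on the windows of 30 days or discharge, whichever is longer.** Under the same stay model, the chance that a SAVR subject stays beyond day 30 runs from 1 − Φ(ln(30/8)/0.40) = 0.05% to 1 − Φ(ln(30/9)/0.45) = 0.37%. That is at most 3 of 800 subjects.

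**The case against.** Several points on the other side are sound.

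- **Consequence.** Endpoint 16 is not in the C.6.10.1 list. C.6.10 says that objectives outside the list will not support labelling claims. This stands. However, section M commits the sponsor to disseminating all secondary results, and under C.5.4 the DSMB may look at safety-related secondary endpoints, so the comparison will be read.
- **Cover elsewhere.** Endpoint 15 compares strokes by severity, and TIAs, at 30 days regardless of discharge. This stands for stroke and TIA. Encephalopathy is not in endpoint 15, and endpoint 16 is its only specified between-arm comparison.
- **Timing.** If nearly all events fall in the first day, the bias almost disappears. This is true, and the documents do not settle the timing.
- **Match to the examination.** The cut-off coincides with the full neurological assessment at discharge or day 7 (C.4.8). That explains the wording but does not equalise the arms.
- **Reading.** The text could mean status at that examination instead of events up to it. An earlier TAVI examination might then find more unresolved encephalopathy, so the direction would be uncertain. The cumulative reading is more natural, especially for TIA, and the direction stated here depends on it.

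A reader might also infer that items 13–16 of C.6.10.1, such as "Incidence of MACCE at 30 days or hospital discharge, whichever is longer", share the defect because long-stay SAVR subjects are followed past day 30. The documents do not support acting on that. Those windows give everyone at least 30 days, very few subjects would exceed it under the stay model above, and C.6.8.1 already plans 30-day estimates of MACCE, MAE components and strokes.

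**Conclusion.** The point holds for endpoint 16. As written, and read as a cumulative count, the endpoint favours TAVI at equal daily risk if TAVI subjects go home before day 7 and before SAVR subjects, and if some events fall in the gap. The first condition is the protocol's own expectation; the second is plausible but not documented.

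The direction is firm under those conditions; the size is not. It could be a couple of percentage points with a materially raised chance of a false finding, or almost nothing, depending on event timing and risk. The false-positive figures also rest on a borrowed prior and threshold.

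The practical exposure is mainly encephalopathy. A reader might infer that the primary result or a labelling claim is affected; neither depends on endpoint 16. The change is worth making because it is cheap and removes unequal counting time from a safety comparison.

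**What to change.** Define endpoint 16 as any stroke, TIA or encephalopathy from the index procedure through day 7, in both arms, whether or not the subject has been discharged. State explicitly that it is a cumulative count. Keep the discharge-truncated proportion as a supportive summary. Leave items 13–16 of C.6.10.1 as they are.

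The cost is a change to the endpoint definition and its programming. Adverse events are already collected through 24 months, so no visit or extra subject is needed, and the primary analysis and labelling hierarchy are untouched.

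One limitation should be stated with the result. After discharge, detection depends on adverse event reporting until the 30-day visit, where only the NIHSS is scheduled (C.4.9.1). Mild confusion or delirium at home may be missed. The fixed window equalises time at risk but not detection, so some bias towards TAVI may remain.
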